Appendix 6 SAS Codes for Statistical Analysis

| Test | Template SAS Code for Modeling (SAS Version 9.4) |
|--|--|
| Determination of lower O'Brien-Fleming stopping boundary for the primary efficacy endpoint at the interim analysis | Proc Seqdesign errspend plots=all boundaryscale=pvalue; PrimaryEfficacy: design alpha = 0.05 beta = 0.20 alt = twosided /* two-sided test*/ nstages = 2 method (reject)= errfuncobf /* O'Brien-Fleming as implemented by Lan-DeMets */ info = cum(24 52) /* information proportion are based on 24 wks out of 52 wks*/; run; |
| Primary Analysis: Stratified Wilcoxon rank-sum test | proc npar1way data=ITT; Title 'Primary Endpoint – Comparison of Annualized VOC Rates'; Title2 'Intent To Treat Population'; class TRT; var ARVOC; strata <stratification factors: REGION HU >; run; |
| Negative binomial regression | proc genmod data=ITT; Title 'Sensitivity Analysis for Primary Endpoint – Negative Binomial Regression'; class TRT <stratification factors: REGION HU >; /*TRT is treatment group; model Y = TRT <stratification factors: REGION HU> / dist = negbin link = log offset = LTIME; /*Y is the count of VOC, LTIME is the log of exposure time in years; lsmeans TRT / cl diff exp; |
| Time to Event Analysis | proc lifetest data=ITT plots=(survival(nocensor atrisk cb)); Title 'Secondary Endpoint – Time to Event Analysis Time to first VOC'; time TIME*VOC(0); Strat TRT; run; |
| Mixed model repeated measures (MMRM) | proc mixed data=ITT; class SUBJECT TRT VISIT HU REGION; model CFB = TRT VISIT TRT*VISIT BASELINE HU REGION; /*CFB=change from baseline; repeated VISIT/ TYPE = UN ddfm=kr sub=SUBJECT; /*Type=CS and then Type AR(1) will be used if UN does not work*/ lsmeans TRT*VISIT/cl diff alpha=0.05; lsmeans TRT/cl diff alpha=0.05; run; |
| Multiple Imputation for the annualized rate of VOCs | proc mi; class TRT REGION HU ; fcs reg(AVOC = TRT REGION HU VOC_O DUR); /*AVOC= annualized VOC rate; VOC_O =Number of observed VOCs; DUR = Duration in the study. run; |

| Test | Template SAS Code for Modeling (SAS Version 9.4) |
|--|---|
| with FCS Method | |
| Negative binomial regression based on Multiple Imputed dataset | <pre>proc genmod data=MIDATA; by _imputation_; class TRT REGION HU ; /*TRT is treatment group; model Y = TRT REGION HU / dist = negbin link = log offset = LTIME; *Y is the count of VOC, LTIME is the log of exposure time in years; lsmeans TRT / cl diff exp; run;</pre> |
| Combine Parameter Estimates | <pre>proc mianalyze data=outreg; modeleffects TRT; /*TRT is the variable for mean treatment differences*/ stderr TRTERR; /*TRTERR is the standard errors for treatment differences*/ run;</pre> |

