13.4. Efficacy Analyses

Primary Efficacy Analysis

The primary efficacy endpoint, annualized rate of VOCs, will be analyzed using a stratified Wilcoxon rank-sum test based on stratification factors of region (North America/Europe versus Africa/Middle East) and HU use (Yes versus No) to compare the treatment effect of the highest tolerated dose of IMR-687 to placebo. VOCs are defined for this study in Inclusion Criterion 3 (Section 8.1). An IA will be performed after all randomized subjects have reached Week 24 or terminated early. A Lan-DeMets alpha spending function will be used to determine the significance levels for the IA to maintain an overall type I error rate of 5% for 2-sided tests.

Secondary Efficacy Analyses

The first key secondary efficacy endpoint, time to first VOC, will be analyzed using a stratified log rank test (stratification factors of HU use and region) and stratified Cox regression model to compare the treatment effect of the highest tolerated dose of IMR-687 to placebo.

The second key secondary efficacy endpoint, proportion of HbF responders (defined as the proportion of subjects with an absolute increase of $\geq 3\%$ in HbF from baseline) at Week 24, will be analyzed using a stratified Cochran-Mantel-Haenszel (CMH) test based on stratification factors of HU use and region to compare the highest tolerated dose of IMR-687 to placebo.

Other secondary endpoints that will be tested at the highest tolerated dose include the following:

- Proportion of VOC-free subjects
- Annualized rate of hospitalizations for VOCs
- Time to second VOC
- Proportion of HbF responders (defined as the proportion of subjects with an absolute increase of $\geq 3\%$ in HbF from baseline) at Week 52
- Change from baseline in HbF (%) and F-cells (%) at Week 24 and Week 52
- Proportion of Hb responders (defined as the proportion of subjects with an increase of ≥ 1.0 g/dL in total Hb from baseline) at Week 24 and Week 52
- Change from baseline in total Hb (g/dL) at Week 24 and Week 52

- Change from baseline in biomarkers of RBC hemolysis (% and absolute reticulocytes, unconjugated [indirect] bilirubin, and LDH) at Week 24 and Week 52
- Change from baseline in each measured subdomain of the ASCQ-Me® questionnaire at Week 24 and Week 52
- Change from baseline in total preference score and individual domain scores of the PROPr questionnaire at Week 24 and Week 52
- Change from baseline in overall score of the SCSES at Week 24 and Week 52

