13.5 Endpoint Analyses

13.5.1 Summary of Analyses

Primary efficacy endpoint, safety endpoints, secondary efficacy endpoints, and corresponding analysis methods are summarized in [Table 7](#) below. Exploratory analyses are detailed in [Section 13.5.5](#).

Table 7 Summary of Efficacy and Safety Analyses

| Endpoints | Analysis Time Points | Analysis Methods | Analysis Set | Time Point for analysis |
|--|---|--|--|-------------------------|
| Primary Efficacy • Annualized rate of VOCs | NA | Comparison of median differences among treatment groups using Stratified Wilcoxon rank-sum tests, with stratification factors of region and HU use. The van Elteren test may be used for the evaluation of treatment difference across strata. P-values for each active group (including pooled IMR-687) vs. placebo | ITT as primary analysis set, mITT, PP as sensitivity | IA, FA |
| Safety | NA | Descriptive statistics | Safety | IA, FA |
| Secondary Efficacy | | | | |
| • Time to first VOC • Time to second VOC | NA | Stratified log rank test, and stratified Cox regression model. p-values from a stratified log rank test and hazard ratios (with 95% CIs) estimated from a stratified Cox regression model with treatment arm and stratification factors of region and HU use as covariates will be provided for comparison of each active group (including pooled IMR-687) vs. placebo | ITT as primary analysis set, mITT, PP as sensitivity | IA*, FA |
| • Annualized rate of VOC-related hospitalizations • Annualized rate of days hospitalized for VOC-related hospitalizations | NA | Stratified Wilcoxon rank-sum tests, with stratification factors of region and HU use. P-values for each active group (including pooled IMR-687) vs. placebo | ITT as primary analysis set, mITT, PP as sensitivity | IA*, FA |
| • Proportion of VOC-free subjects • HbF responder rate at Week 24 and Week 52 • Hb responder rate at Week 24 and Week 52 | NA | Stratified CMH test adjusted for stratification factors of region and HU use. | ITT as primary analysis set, mITT, PP as sensitivity | IA*, FA |

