13.5.3.1 Time to first VOC

The time to first VOC event will be analyzed using Kaplan-Meier methods. Time in months to the first VOC event can be calculated as $([\text{date of first VOC event} - \text{date of first dose} + 1] / 30.4375)$.

Both start and end date of VOC event will be collected from “VOC” CRF page. The start date of the VOC is not expected to be missing and will be used for the analysis. In the rare event the start date is missing, then the end date can be used. If both start date and end date are missing, no imputation will be made and the event will be excluded from the analysis.

Subjects who experience no VOC events during the study will be censored at their study end date (or date cut-off date if the study end date is not available). Using the ITT set, the number and percentage of subjects with events (subjects who experienced at least 1 VOC on-study) and censored (subjects who did not experience any VOCs on-study) will be presented. The 25th, 50th (median), and 75th percentiles, along

with associated 2-sided 95% CIs based on the Brookmeyer and Crowley method will be presented. The p-values from a stratified log rank test and hazard ratios (and 95% CIs) estimated from a stratified Cox regression model with treatment arm and stratification factors (region and HU use) as covariates will be presented for comparison of each treatment group to placebo. Kaplan-Meier curves will be produced for the time to first VOC with separate curves for each treatment group.

Sensitivity analysis will be performed for Time to first VOC using the mITT and PP analysis sets. Major protocol deviations and subjects (or data) excluded from the PP analysis set will be defined by the Sponsor in a blinded manner prior to database lock. No imputation will be performed for the PP analysis.

13.5.3.2 Other sensitivity analyses may be added. All sensitivity analyses will be performed at FA.HbF responder rate at Week 24

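### The SAP's code for time to first VOC runs an unstratified three-arm log-rank test, not the stated stratified test of highest tolerated dose against placebo; the Cox wording is also contradictory

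*SAP*

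**What the plan says.** Protocol 13.4 (Efficacy Analyses) says that time to first VOC "will be analyzed using a stratified log rank test (stratification factors of HU use and region"), together with a stratified Cox model, to compare the highest tolerated dose with placebo. SAP 13.5.3.1 takes "p-values from a stratified log rank test" and hazard ratios "estimated from a stratified Cox regression model with treatment arm and stratification factors (region and HU use) as covariates", for each treatment group against placebo. SAP Table 7 (Section 13.5.1) words the Cox model the same way, for time to first and time to second VOC: "stratified Cox regression model with treatment arm and stratification factors of region and HU use as covariates". SAP 12.3 and 12.4 place time to first VOC second in the fixed sequence, tested at the highest tolerated dose against placebo.

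SAP Appendix 6 has one time-to-event entry. It opens with "proc lifetest data=ITT plots=(survival(nocensor atrisk cb" and its analysis statements are "time TIME*VOC(0); Strat TRT; run". A title statement in that code labels it as the secondary analysis of time to first VOC. No Cox code is given.

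**The concern.** In PROC LIFETEST, the variables in the STRATA statement define the groups compared unless a GROUP= option is given. With treatment alone in that statement and no arm filter, the procedure tests equality of all treatment curves at once and makes no allowance for region or HU use. The entry therefore departs from the text twice: it is unstratified, and it covers three arms instead of two.

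Step 2 gates everything below it in the sequence. A programmer who follows the appendix would obtain a p-value for the hypothesis that all three arms are equal, and that p-value can respond to the lower dose.

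The Cox wording has its own problem. A stratified model gives each region-by-HU cell its own baseline hazard. A covariate model uses one baseline hazard and estimates effects for region and HU use. The text names both, and no code settles which is meant.

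**Working it through.** **Text against code**

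| Feature | Protocol 13.4; SAP 13.5.3.1 and Table 7 | SAP Appendix 6 |
|---|---|---|
| Stratified by region and HU use | Yes | No; treatment is the only strata variable |
| Arms in the step 2 test | Highest tolerated dose and placebo | Whole ITT set: 49 + 35 + 31 = 115 subjects in three arms |
| Degrees of freedom | 2 − 1 = 1 | 3 − 1 = 2 |
| Cox model | Called stratified; strata listed as covariates | No code |

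The primary-analysis, negative binomial, MMRM and imputation entries in the same appendix all name region and HU. The time-to-event entry does not. The spelling of the strata statement in the code is treated as a typing slip, and nothing here rests on it.

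The documents give no power or event figure for this endpoint, so there is nothing to reproduce. What follows is an illustration.

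**Inputs from the SAP (8.1.2).** Arms of 31 placebo, 49 higher dose and 35 lower dose. Planning rates of 5.0 and 3.0 VOCs per year, read here as constant hazards, so the hazard ratio is 3.0 / 5.0 = 0.6.

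**Inputs assumed.** Exponential times; one year of follow-up; no dropout; four strata of equal probability. Stratum multipliers on the base rate of 5 per year are 1/k, 1/√k, √k and k, with k = 1 (no effect), 1.5 or 2. Lower-dose hazard ratios are 0.6, 0.8 or 1.0. Two-sided level 0.05.

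**Statistic.** Summed over strata, U = Σ(observed − expected events) per arm, with hypergeometric-type variance V. The test statistic is U′V⁻¹U, referred to chi-square on (number of arms − 1) degrees of freedom. The unstratified version treats all subjects as one stratum.

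**Rejection rates, 4,000 trials per row**

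| HR higher / lower; k | Stated: stratified, two arms | Unstratified, two arms | Coded: unstratified, three arms |
|---|---|---|---|
| 1.0 / 1.0; 2 | 5.3% | 5.6% | 5.9% |
| 0.6 / 0.8; 1.5 | 54.1% | 52.7% | 44.4% |
| 0.6 / 0.8; 2 | 52.6% | 44.2% | 36.4% |
| 0.6 / 0.6; 2 | 51.6% | 43.1% | 41.1% |
| 0.6 / 0.6; 1 | 54.4% | 60.4% | 56.7% |
| 0.6 / 1.0; 1 | 53.3% | 59.4% | 66.6% |
| 1.0 / 0.6; 2 | 4.9% | 5.0% | 42.4% |

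The simulation standard error is about √(0.526 × 0.474 / 4,000) = 0.8 percentage points. Repeat runs of the third row gave values within one or two points (for example about 54% and 35%).

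In the third row, dropping the strata costs 52.6 − 44.2 = 8.4 points, and adding the third arm costs a further 44.2 − 36.4 = 7.8. In the last row almost all of the excess comes from the third arm, because the two-arm tests stay near 5% with or without strata.

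**The case against.** The strongest reply is that the intended test is not in doubt. The protocol synopsis, Protocol 13.4, SAP Table 7 and SAP 13.5.3.1 all state the stratified test, against one row in a table of template code. That row also has an innocent use: SAP 13.5.3.1 asks for Kaplan-Meier curves by treatment group, and LIFETEST with treatment as the strata variable draws them. The appendix is visibly incomplete, with no Cox, CMH or ANCOVA code, so the stratified test may simply have been left out. The missing arm filter is not peculiar to this row either; the primary-analysis template also runs on the whole ITT set.

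Much of this stands. It makes the defect an inconsistency to reconcile, not an absent specification. It does not remove the defect. SAP 6.0 ranks the SAP above the protocol, but nothing ranks SAP text above SAP code, and this is the only code given for the endpoint.

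Three stronger readings are tempting, and the documents do not support them.

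- A reader might infer that the coded test is conservative or always loses power. It is not so in general: it rejects more often than the stated test in the fifth, sixth and last rows of the table.
- A reader might take 42% as the trial's false-positive rate. It is the rejection rate of the step 2 test taken alone, under one assumed scenario, and step 2 is reached only after the primary endpoint has succeeded.
- A reader might think that the Cox wording changes the confirmatory p-value. Both SAP passages take that p-value from the log-rank test.

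**Conclusion.** The point holds as a mismatch between text and code on the first key secondary endpoint, and it should be corrected. As coded, step 2 would test whether any of the three arms differ, without stratification, and a lower-dose effect alone could carry it.

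The size depends on assumptions, because the documents give neither the prognostic strength of region and HU use nor a lower-dose effect. With stratum hazards of 0.5 to 2.0 times the base rate, the coded test gives about 36% where the stated test gives 53% (hazard ratios 0.6 and 0.8). It gives about 42% where the stated test gives 5% (higher dose equal to placebo, lower-dose hazard ratio 0.6). With no stratum effect the direction of the power difference reverses. The existence of the mismatch depends on none of these assumptions.

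The contradictory Cox wording is a lesser matter, confined to the reported hazard ratio and confidence interval.

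**What to change.** Before treatment codes are opened for the interim analysis:

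- In Appendix 6, code the test as `strata REGION HU / group=TRT` on a data set restricted to the two arms compared. Keep a separate call with treatment as the only strata variable for the Kaplan-Meier plots.
- Add PHREG code with `strata REGION HU` and treatment in the model statement, to match the stratified model that the text names.
- In SAP 13.5.3.1 and Table 7, stop describing region and HU use as covariates of that model.
- Apply the same to time to second VOC. Protocol 13.4 covers time-to-event endpoints in general with a log-rank test and does not mention strata; SAP Table 7 stratifies.
- Add a sentence saying that SAP text governs over template code.

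This takes a few lines of code and wording. The statistical price is some power if the strata are not prognostic: in the two rows with k = 1, the stratified two-arm test loses 60.4 − 54.4 = 6.0 and 59.4 − 53.3 = 6.1 points against the unstratified two-arm test. The protocol and SAP text already accepted that price by choosing stratification.

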- Change from baseline in biomarkers of adhesion such as soluble E-sel, P-sel, ICAM-1, and VCAM-1 at Week 24 and Week 52
- Change from baseline in biomarkers of inflammation such as hsCRP and MPO at Week 24 and Week 52
- Change from baseline in biomarkers of cardiac stress such as NT-proBNP at Week 24 and Week 52
- Change from baseline in RBC indices, such as MCV, at Week 24 and Week 52

The secondary endpoints of proportion of HbF responders at Week 52 and proportion of Hb responders at Week 24 and Week 52 will each be analyzed in a similar manner as the second key secondary efficacy endpoint using a stratified CMH test based on stratification factors of HU use and region.

The annualized rate of hospitalizations for VOCs will be analyzed using a stratified Wilcoxon rank-sum tests based on stratification factors of HU use and region.

Change from baseline endpoints for continuous variables will be analyzed using mixed models for repeated measures (MMRM) with treatment, visit, and treatment-by-visit interaction as fixed effects, and baseline value, HU use, and region as covariates. Unstructured covariance matrices will be used. If there are convergence problems, then the use of other covariance matrices will be considered as appropriate.

Time-to-event endpoints will be analyzed using log-rank tests, and Kaplan-Meier plots will be provided.

An FA will be conducted at study completion (i.e., when all subjects have reached Week 56 or terminated early). A Lan-DeMets alpha spending function will be used to determine the significance levels for the IA and FA to maintain an overall type I error rate of 5% for 2-sided tests. At the FA endpoints will be tested in a sequential hierarchical order at the highest tolerated dose.

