10.2 Definitions of Baseline and Change from Baseline Values

Unless otherwise specified, baseline is defined as the last non-missing measurement prior to the first dose of study drug.

All ECG assessments at a visit are to be performed in triplicate at each scheduled visit. The baseline value for ECG parameters will be derived as the average of all non-missing values, at the last visit prior to the first dose of study drug. Post-baseline assessments at a visit will be averaged for analysis.

In analyses of pharmacodynamics (PD) parameters, baseline is defined as the average of non-missing values from the screening and baseline visits. PD assessments include the following laboratory measurements based on blood samples (HbF-associated biomarkers and total Hb; biomarkers of RBC hemolysis, adhesion, inflammation, and cardiac stress; RBC indices).

Change from baseline at a post-baseline visit is defined as follows:

- For the ECG parameters: Post-Baseline Average Value – Baseline Average Value
- For PD parameters: Post-Baseline Value – Baseline Average Value
- For all other parameters: Post-Baseline Value – Baseline Value

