Annualized rate of days hospitalized for VOC-related hospitalization will be analyzed in the same way as annualized rate of VOC-related hospitalization.

Time to first for VOC-related hospitalization

The time to first VOC-related hospitalization event will be analyzed using Kaplan-Meier methods. Time in months to the first VOC-related hospitalization event can be calculated as ([date of first VOC-related hospitalization event – date of first dose + 1] / 30.4375).

Time to second VOC

This analysis of time to second VOC event will be analyzed using Kaplan-Meier methods similar to the analysis of the time to first VOC. A patient with less than two VOCs before withdrawal or completion of the study is considered censored at the time of withdrawal or completion of the study.

A sensitivity analysis will be performed separately, excluding these subjects without any VOCs.

HbF responder rate (as defined by proportion of subjects with an absolute increase of $\geq 3\%$ in HbF from baseline) at Week 52

This analysis of HbF responder at Week 52 will be similar to the HbF responder rate analysis at Week 24 ([Section 13.5.3.2](#)). Similar imputation rules will apply:

1. Subject will be treated as a non-responder if there is an initiation of HU post randomization and prior to Week 52.
2. HbF value from Week 36 (the last scheduled visit before the target analysis visit) will be used when Week 52 value is missing,
3. Any HbF value within 8 weeks (56 days) of RBC transfusion is excluded from all analyses.

Change from baseline in HbF (%) and F-cells (%) at Week 24 and Week 52

Change and percentage change from baseline in HbF (%) and F-cells (%) will be analyzed using mixed models for repeated measures (MMRM) with baseline value as a covariate, fixed effects for region (North America/Europe vs. Africa/Middle East), HU use (yes vs. no), treatment, visit, and treatment-by-visit interaction. Unstructured covariance matrices will be assumed for all models, but auto-regressive 1 (AR1) and compound symmetry (CS) may also be assessed (in that order) if the unstructured covariance matrix does not converge.

Values used at the visit and change from baseline for each parameter will be summarized for each post-baseline timepoint. The LS Mean estimates and 95% CIs will be displayed for all treatment groups. LS Mean difference estimates and 95% CIs with p-values for all IMR-687 treatment groups (relative to placebo) will be provided.

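### The MMRM holds the baseline slope constant across visits; if that slope changes over time, the Week 52 treatment differences lose some precision, and a baseline-by-visit term would prevent this at almost no cost.

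*SAP*

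**What the plan says.** The MMRM covers change (and percentage change) from baseline in HbF, F-cells, total Hb, hemolysis markers, adhesion and inflammation markers, the cardiac marker and MCV. Four places specify it, and they agree on the mean model:

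- SAP Appendix 6, code: "model CFB = TRT VISIT TRT*VISIT BASELINE HU REGION".
- SAP 13.5.4, text: "mixed models for repeated measures (MMRM) with baseline value as a covariate, fixed effects for region", followed by HU use, treatment, visit and treatment-by-visit.
- SAP Table 7: the same terms.
- Protocol 13.4 (repeated in the synopsis): "treatment, visit, and treatment-by-visit interaction as fixed effects, and baseline value, HU use, and region as covariates".

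The only interaction with visit is that of treatment. On covariance, SAP 13.5.4 says "Unstructured covariance matrices will be assumed for all models", with simpler structures if the model does not converge. The contrasts reported are by visit ("lsmeans TRT*VISIT/cl diff alpha=0.05"), and Weeks 24 and 52 are the endpoints. For these laboratory variables, SAP 10.2 sets a special baseline: "baseline is defined as the average of non-missing values from the screening and baseline visits". SAP Table 2 gives seven post-baseline analysis visits: Weeks 4, 8, 12, 16, 24, 36 and 52.

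**The concern.** The regression of change on baseline need not be the same at Week 4 as at Week 52. At visit t its slope is ρ_t × (SD_t / SD_baseline) − 1, where ρ_t is the correlation of the visit value with baseline. If correlation weakens over a year while the spread stays the same, the slope is shallow early and steep late. A model with one slope must compromise. Under an unstructured covariance the compromise leans towards the early visits, where residual variance is small. Week 52 is then under-adjusted: part of what baseline could explain stays in the residual.

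At stake is the width of the Week 52 intervals in arms of about 49 (higher dose) and 31 (placebo), with enrollment already complete. In the final fixed sequence (SAP 12.4) the Week 52 contrasts for these endpoints are formal steps, and the first failure makes all later p-values nominal.

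**Working it through.** **Stated figures.** The only relevant power figures are for the primary Wilcoxon test (SAP 8.1.2). They reproduce: the stated 88% comes out at 87.6–88.6%, and the 78% with dropout at 77.5–78.8%, using a noncentral-t calculation with the Wilcoxon efficiency 3/π and a difference of 2.0 or 2.034. The documents give no SD, correlation, standard error or power for any MMRM endpoint, so no stated figure bears on this point.

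**Inputs from the documents.** Arms 49/35/31 and 25% dropout (SAP 8.1.2); the seven visits (SAP Table 2); baseline as the mean of two values (SAP 10.2); unstructured covariance.

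**Assumed inputs.** Total variance 1 at each visit. A share of 0.95 is signal (0.80 in the noisier cases). Of the signal, a stable part (0.7 mild, 0.4 moderate, 0 strong) persists, and the rest decays as exp(−weeks apart/52), or /26 in the very strong case. Screening is 3 weeks before Day 1.

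**Formulas.** Let b be the vector of visit-specific slopes of change on baseline and S the residual covariance given baseline. With complete data the common slope tends to

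β = (1′S⁻¹b) / (1′S⁻¹1),

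and the variance of the treatment difference at visit t, relative to the model with `BASELINE*VISIT`, is

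VR_t = 1 + (b_t − β)² × Var(baseline) / S_tt.

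**Moderate decay, Week 52.**
- Var(baseline) = (1 + 0.918)/2 = 0.959.
- Covariance of baseline with the Week 52 value = (0.590 + 0.578)/2 = 0.584.
- Slope b = 0.584/0.959 − 1 = −0.391.
- S = 1 − 0.584²/0.959 = 0.645.
- β = −0.120.
- VR = 1 + (0.271)² × 0.959/0.645 = 1.109, so the SE ratio is √1.109 = 1.053.

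| Assumed pattern | Correlation with Day 1, Wk 4 / Wk 52 | Slope at Wk 52 | Common slope | VR Wk 24 | VR Wk 52 | SE ratio Wk 52 | Simulated SE ratio Wk 52 |
|---|---|---|---|---|---|---|---|
| Constant | 0.70 / 0.70 | −0.176 | −0.176 | 1.000 | 1.000 | 1.000 | 0.999 |
| Mild decay, noisier | 0.78 / 0.65 | −0.277 | −0.175 | 1.002 | 1.017 | 1.009 | not run |
| Mild decay | 0.93 / 0.77 | −0.207 | −0.075 | 1.012 | 1.043 | 1.021 | 1.005 |
| Moderate decay | 0.91 / 0.59 | −0.391 | −0.120 | 1.031 | 1.109 | 1.053 | 1.066 |
| Strong decay, noisier | 0.74 / 0.29 | −0.674 | −0.317 | 1.019 | 1.124 | 1.060 | not run |
| Strong decay | 0.88 / 0.35 | −0.642 | −0.193 | 1.055 | 1.217 | 1.103 | 1.116 |
| Very strong decay | 0.81 / 0.13 | −0.868 | −0.376 | 1.060 | 1.227 | 1.108 | not run |

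The simulations used 600 trials per pattern, the planned arm sizes, 25% dropout completely at random, HU and region in the model, and maximum likelihood without the Kenward-Roger adjustment. Mean errors of the two models were alike and at most about 0.02 SD. Other decaying patterns with equal variances gave Week 52 inflation of about 4–16%.

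**Growing spread.** Let the SD rise linearly by 25% or 50% to Week 52. The moderate case falls from 10.9% to 2.7% or 0.2%, because the larger SD_t offsets the smaller ρ_t. With correlation constant at 0.70, the same growth changes the slope by itself and costs 2.5% or 8.2%.

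**Later visits only.** The CV marker (presumably NT-proBNP) is sampled after baseline only at Weeks 12, 24, 36 and 52. On that grid the moderate case falls from 10.9% to 5.1%.

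**Effect on a test with 80% power.** Power becomes Φ(2.802/√VR − 1.960): 78.3% at VR 1.043, 75.8% at 1.109 and 73.9% at 1.16.

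**The case against.** The case against is substantial. This is a consistent, prespecified model and not a coding slip, and no type I error problem follows from it. The loss rests on an assumption. A reader might infer that the influence of baseline on change does grow over the year, and so that the Week 52 differences will be less precise. The documents do not support that: they state no slope, correlation or variance, and with constant correlation and constant spread the planned model loses nothing. Falling correlation does not by itself imply a steeper slope either, since the drug may widen the spread of HbF.

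A reader might also infer that a chance baseline imbalance, only partly removed, biases the Week 52 result. Under randomization such imbalance is part of the sampling variance, and the simulations showed no material bias.

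Two SAP rules may reduce the loss further. Carried-forward HbF values (Week 16 for Week 24, Week 36 for Week 52) enter the MMRM, and the Week 52 window opens at Day 310. The effect on the testing sequence is also remote: by the ordering rule in SAP 12.4, the first Week 52 MMRM contrast comes after seven non-MMRM endpoints and two Week 24 contrasts.

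All of this stands, and it limits the point to a conditional one. It does not defend the constant slope. The SAP gives no reason for that restriction, and lifting it costs practically nothing when it happens to be true (simulated SE ratio 0.999).

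**Conclusion.** The point holds as a conditional loss of efficiency. If the baseline slope changes over time, the Week 52 variance is roughly 0–16% larger than the same data allow, usually a few percent on the SE, and the Week 24 variance is 0–4% larger. The two steepest patterns, with low measurement error and a Week 52 correlation of 0.35 or 0.13, reach 22–23% at Week 52 and about 6% at Week 24. I treat them as outer cases, though the documents cannot exclude them. When correlation decays, growing outcome variance or a late-visit grid makes the loss smaller.

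The range rests on assumed correlations and large-sample formulas for complete data. The simulations covered only dropout completely at random. Bias is not at issue. The primary endpoint, time to first VOC, the HbF responder rate and the QoL scores that Table 7 puts under ANCOVA are untouched.

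**What to change.** Before interim unblinding:

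- Add `BASELINE*VISIT` to the model statement of the MMRM code in SAP Appendix 6.
- Add a baseline-by-visit interaction to the MMRM description in SAP 13.5.4 and Table 7.
- Align the MMRM sentence in the protocol synopsis and protocol 13.4, or record the difference in the SAP. SAP 6.0 already lets the SAP prevail.

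Interim unblinding is the right deadline, rather than final database lock, because SAP 12.3 releases group results to the blinded team at the end of the interim analysis.

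The cost is one extra slope per additional visit: six with seven visits, three for a marker sampled at four. With 115 subjects randomized this is affordable. No new data are needed, and essentially nothing is lost if the interaction proves unnecessary.
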